5.2. Risks of Investigational Product or Intervention cited in Medical Literature

Not Applicable

5.3. Risks of Other Protocol Specified Medications

Not Applicable

5.4. Risks of Study Procedures

1. Pediatric clinicians: There are no risks to pediatric clinicians due to any procedure in this trial.
2. Infants/caregivers: There is a risk of breach of confidentiality. There are no additional risks to infants due to any procedure in this trial compared to not participating in the study (all clinical procedures outlined in the PPA Guidelines are considered standard of care and the infants are not subject to any of those procedures as a result of study participation).

5.5. Potential Benefits

1. The iREACH intervention may improve the clinical decision making process of pediatric clinicians around peanut allergy risk assessment and counseling of caregivers and may lead to increased implementation of guidelines-based peanut product introduction.
2. If the intervention improves adherence to the PPA Guidelines, the following benefits may be seen:
 - a. Improved identification of infants at risk for peanut allergy by pediatric clinicians.
 - b. Prevention of unnecessary referrals to allergy specialists for infants at low-risk for peanut allergy.
 - c. Reduction in allergic reactions to peanut introduction in the home setting through improved identification of infants at risk for allergic reactions.
 - d. Improved confidence of caregivers regarding peanut introduction for prevention of peanut allergy.
 - e. Reduction in the incidence of peanut allergy in children.

6. Investigational Agent /Device/Intervention

6.1. Investigational Agents/Devices/Interventions

6.1.1. Investigational Intervention: Intervention to Reduce Early (Peanut) Allergy in Children (iREACH)

The iREACH intervention consists of **A) an education module** about the PPA Guidelines and the research on which the guidelines were based; **B) an EHR-integrated CDS tool** in the 4- and 6-month WCC templates to support pediatric clinician decision-making around 1) proper triage of infants into peanut allergy risk categories, 2) allergy testing and interpretation and/or allergist referral for high-risk infants, and 3) caregivers counseling on peanut introduction including educational materials for families

and a minor addition to the anticipatory guidance section of the note template to facilitate documentation of PPA Guidelines discussion; and **C) follow-up prompts** in the 9- and 12-month WCC templates guiding pediatric clinicians to ask caregivers about inclusion of peanut products in their child's diet. The components of the intervention are detailed below:

A. Education Module: Text- and video-based educational materials covering the PPA Guidelines, the research on which the guidelines were based, and instructions for using the iREACH CDS tool will be delivered as an online module. Pre-and post-test knowledge surveys will be embedded into the module and permits monitoring of provider compliance with the assigned training. Key study personnel will be available via email, phone, or in-person to answer any questions that arise after completion of the educational module posttests.

B. CDS Tool: A multi-component tool within the EHR that includes the following:

- a. *A Best Practice Advisory (BPA)* will be triggered at 4- and 6-month well child visits to remind pediatric clinicians to evaluate child for peanut product introduction.
- b. *A Smart List* within note template to remind pediatric clinicians to assess the infant for conditions that would classify the infant as high-risk for PA (i.e., egg allergy or severe eczema).
- c. *A Smart Set* (order set) to guide the pediatric clinician in choosing peanut sIgE or allergist referral based upon PA risk status. The pediatric clinician selects orders based upon their assessment of PA risk. This Smart Set includes the option to print out a caregiver educational handout to assist with caregiver counseling on peanut product introduction.
- d. *A BPA* triggered when the pediatric clinician views peanut sIgE results (for those patients for whom sIgE has been ordered. The BPA will provide the criteria for "positive" results (≥ 0.35 kU/L) and a recommendation to refer to an allergy specialist if results are positive.

Caregiver Handout on How to Introduce Peanut Containing Products: Handout adapted from the NIAID caregiver materials (English and Spanish versions). The handouts were simplified and tested with caregiver groups including low-literacy, underserved families. This handout can be used as part of pediatric clinician counseling and can go home with caregivers as a reminder.

C. Follow-up Prompts at 9- and 12-month WCC: *Smart Texts and Data Elements* that advise the pediatric clinician to ask caregivers and chart whether peanut products have been introduced into their infant's diet. If the caregiver reports that peanut products were introduced, the clinician will be directed to document whether introduction was tolerated. If caregiver reports that peanut products were not introduced, the clinician will be directed to ask the caregiver for reasons why they did not.

Note: For those practices that do not use an Epic-based EHR, Lurie Children's study team will facilitate and work with their informatics teams to implement an iteration of the CDS tool that is compatible with the practice EHR.

6.1.1.1. Formulation, Packaging, and Labeling

Not Applicable

6.1.1.2. Dosage, Preparation, and Administration

Not Applicable

6.1.2. Control Arm

Pediatric clinicians in practices that will be randomized to the control arm will provide standard care.

Following the completion of data collection for the primary outcome, practice sites in the control arm will be offered the iREACH intervention. This will not affect the outcome of any of the primary, secondary, or exploratory analyses.

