| Primary Endpoint(s) | 
 Percent of infants at low risk for peanut allergy whose pediatric clinicians adhered to the guidelines. Percent of infants at high risk for peanut allergy whose pediatric clinicians adhered to the guidelines. |
| Secondary Endpoint(s) | 
 Percent of infants at low risk for peanut allergy who developed peanut allergy by age 2.5. Percent of infants at high risk for peanut allergy who developed peanut allergy by age 2.5. 
(Exploratory Objectives)
 
 Allergist adherence to the PPA Guidelines Barriers/facilitators for PPA Guideline adherence among pediatric clinicians and caregivers. Caregiver adherence to PPA Guidelines (peanut product introduction and feeding frequency). |
| Accrual Objective | Pediatric clinicians: 200; High-risk infants: 500; Low-risk infants: 10,000; Caregivers: 10,500 |
| Study Duration | 51 months for practices, maximum 23 months for pediatric clinicians, maximum 26 months for infants and caregivers |
| Treatment Description | The iREACH intervention consists of A) an education module on the PPA Guidelines and the research on which the guidelines were based; B) an EHR-integrated CDS tool in the 4- and 6-month WCC templates to support pediatric clinician decision-making around 1) proper triage of infants into peanut allergy risk categories, 2) allergy testing and interpretation and/or allergist referral for high-risk infants, and 3) caregiver counseling on peanut introduction including educational materials for families; and C) follow-up prompts in the 9-and 12-month WCC templates guiding pediatric |

| | |
|---------------------------|--|
| | clinicians to ask caregivers about inclusion of peanut products in their child's diet. |

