3.2. Description of Study Design

[figure not shown]
This study is a two-arm, cluster-randomized, controlled clinical trial. A minimum of 30 pediatric practice sites will be randomized to the iREACH intervention arm or to the control arm (**Figure 3**). All pediatric clinicians within each participating practice (n≈200 total) will be assigned to the arm to which their practice is randomized. Pediatric clinicians in the intervention arm will 1) receive the iREACH education module, 2) have the iREACH CDS tool integrated into the EHR templates for use at the 4-, 6-, 9-, 12-month WCC, and 3) will be reminded by EHR-embedded prompts at the 9-month WCC to ask caregivers whether peanuts were introduced and tolerated.

No study procedures will be implemented in the non-intervention, control practices, and their pediatric clinicians will not receive extra PPA Guidelines education, nor will any EHR modifications be made in their practices to support adherence to PPA guidelines. The trial will be conducted over an 18-month period. During this time, approximately 500 high-risk infants and 10,000 low-risk infants are expected to be seen for 4- and 6-month WCC. The primary outcome, pediatric clinician adherence to the PPA Guidelines, will be assessed using EHR data for each infant following the 6-month WCC.

Data for the secondary outcome will be obtained by a combination of EHR data extracted after the infant's 6-month WCC and data collected from caregivers. EHR data extraction will be performed to obtain data from the infant's 9-, 12-, 15-, 18-, 24-month WCC and any sick visits and allergist progress notes entered from 4-30 months of age. Caregivers' data will be collected via surveys of caregivers of children seen for 4- or 6-month WCC visits during the study period. Caregivers will be recruited and asked to provide informed consent at the time of the child's first birthday and questions will be asked to determine the incidence of peanut allergy. A follow-up survey will be sent to caregivers after the child's second birthday.

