Data for exploratory outcomes will be obtained through EHR data extraction and surveys of pediatric clinicians and the caregivers of infants seen for 4- or 6-month WCC. Pediatric clinicians in the intervention arm will be asked to provide informed consent and will complete three surveys over approximately 21 months. Pediatric clinicians in the control arm will be asked to provide informed consent following completion of data collection for the primary outcome and will complete one survey. Finally, caregivers, through the two surveys conducted at the time of their child's first and second birthdays, will provide information for exploratory outcomes.

Figure 3. iREACH Study Design

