For low-risk infants, pediatric clinician adherence will be determined based on whether a recommendation for dietary peanut introduction was given. This information will be obtained from pediatric clinician notes made in the anticipatory guidance section using NLP. If the information is absent from these sources, other sources will be utilized (i.e., caregiver surveys) to complement EHR data.

Figure 4. Pediatric Clinician Adherence

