8.3. Timeline for Study Activities

Study activities will begin with practice randomization and continue for 18 months of observation.

During the 18-month observation period, all infants that will be seen by pediatric clinicians in participant practices for at least one 4- or 6-month WCC will be considered eligible for EHR data extraction, as long as they (and their caregivers) fulfill inclusion/exclusion criteria. During this period, EHR data will be extracted as described above (Table 8.2). Additional study activities related to the pediatric clinicians that will take place during the same period are described in Table 8.5.1.

For each study infant, information will be obtained through EHR until age 30 months. In addition, activities related to the infant caregivers will take place at 11, 12 and 24 months of the infant's age, as described in Table 8.5.2.

| Table 8.5.1. Schedule of Activities-Practice Sites, Pediatric Clinicians | 18-Month Study Observation Period | | |
|---|--|---------------|------------|
| | Beginning | Middle | End |
| PRACTICES | | | |
| Randomization of Practice Sites | X | | |
| INTERVENTION ARM PEDIATRIC CLINICIANS | | | |
| Pediatric Clinician Informed Consent | X | | |
| Pediatric Clinician Characteristics Questionnaire | X | | |
| Pediatric Clinician Knowledge Attitudes Barriers Facilitators Survey #1 | X | | |
| Pediatric Clinician Knowledge Attitudes Barriers Facilitators Survey #2 | | | X |
| Pediatric Clinician Knowledge Attitudes Barriers Facilitators Survey #3 | | | X |
| CONTROL ARM PEDIATRIC CLINICIANS | | | |
| Obtain Pediatric Clinician Informed Consent | | | X |
| Pediatric Clinician Characteristics Questionnaire | | | X |
| Pediatric Clinician Knowledge Attitudes Barriers Facilitators Survey | | | X |

| Table 8.5.2. Schedule of Activities-Caregivers | Age of Infant | | |
|--|-------------------------|-------------------------|---|
| | Around 12-months | Around 24-months | |
| CAREGIVERS | | | |
| Caregiver Opt-out Letter (if needed based on recruitment method) | | X | |
| Caregiver Informed Consent and Consent to Link Survey with | | X | X |
| Caregiver Characteristics Questionnaire | | X | X |
| Caregiver Feeding, Outcomes Attitudes, Barriers, Facilitators | | X | X |
| Caregiver Account of Clinician Peanut Recommendations, Testing and Introduction Survey | | X | |
| Caregiver Stress, Quality of Life | | X | X |

| | | | |
|--|--|---|---|
| Infant Food Frequency Questionnaire | | X | X |
|--|--|---|---|

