13.4.4 Analyses of Secondary and Other Endpoint(s)

Analysis of the secondary endpoint will be performed separately for high- and low-risk infants. Incidence of peanut allergy will be analyzed with generalized linear mixed models in the PEDI sample in the same manner as the primary pediatric clinician endpoint with infants as the unit of analysis.

Data for diagnosis of peanut allergy (yes/no) from the 4 month - 30 month EHR data collection time points will be combined into one binary variable describing whether (yes/no) diagnosis occurred at any time up through the 30-month time point. Data from caregivers FOABF surveys at 12 and/or 24 months will be used to determine the presence of a caregiver reported peanut allergy or physician diagnosed peanut allergy.

The peanut allergy endpoint will be determined by combining information from EHR and caregiver survey information as described in the MOP.

Exploratory analyses of the secondary peanut allergy endpoint will include the following. Analyses will be treated as exploratory and hypothesis- generating, so no formal correction for multiple testing will be applied.

- The primary analysis of the secondary endpoint will be repeated to evaluate the impact of missing data. Missing data will be classified in three ways as follows:
 - Missing data are not imputed via multiple imputation and are left missing.

- Missing data are imputed as non-peanut allergic.
- Missing data are imputed as peanut allergic.
- The primary analysis of the secondary endpoint will be repeated combining all infants from both the high- and low-risk groups. Risk group and the interaction of risk group and intervention group will be included as fixed effects predictors.
- The primary analysis of the secondary endpoint will be repeated in the PEDI sample including pediatric clinician adherence, allergist adherence (high-risk only), their interaction, and their interactions with intervention group as fixed effects predictors.
- The primary analysis of the secondary endpoint will be repeated in the EEDI2 sample including pediatric clinician adherence, allergist adherence (high-risk only), caregiver adherence, and all two- and three-way interactions with each other and intervention group, as fixed effects predictors.
- The primary analysis of the secondary endpoint will be repeated in the EEDI2 sample including the presence and extent (e.g., duration and amount) of peanut exposure as predictors.

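### The assurance that offering iREACH to control practices affects no analysis is unsupported for peanut allergy to 30 months, and only conditionally supported for caregiver adherence and the clinician survey

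*Combined protocol and SAP*

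**What the plan says.** Under section 6.1.2 (Control Arm), control practices give standard care and are offered iREACH after primary-outcome data collection ends. The section then says: "This will not affect the outcome of any of the primary, secondary, or exploratory analyses". It gives neither a calendar month nor a reason.

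The timings that bear on this are elsewhere:

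- **Primary outcome.** Section 3.2 says it "will be assessed using EHR data for each infant following the 6-month WCC". Section 3.3 refers to assessment after either a 4- or a 6-month well child check (WCC). For low-risk infants it adds "If the information is absent from these sources, other sources will be utilized (i.e., caregiver surveys) to complement EHR data", with a similar provision for high-risk infants. The first caregiver survey is around the first birthday.
- **Eligibility.** Under section 8.3, infants seen in the 18-month observation period "for at least one 4- or 6-month WCC will be considered eligible for EHR data extraction".
- **Peanut allergy.** Section 13.4.4 counts whether a "diagnosis occurred at any time up through the 30-month time point".
- **Caregiver adherence.** Section 13.4.5 judges low-risk infants on introduction by 12 months. High-risk infants whose testing supports introduction are judged on introduction by 7 months and on continued feeding reported around the first birthday.
- **Clinician survey (KABF).** Section 3.2 and Table 8.1 place the single control-arm survey after primary data collection. Table 8.5.1 places it at the end of the 18-month period. Section 13.4.5 compares it with intervention-arm responses.
- **Later-acting content of iREACH.** Section 6.1.1 describes clinician education, and 9- and 12-month prompts "that advise the pediatric clinician to ask caregivers and chart whether peanut products have been introduced".
- **Durations.** The synopsis gives "51 months for practices, maximum 23 months for pediatric clinicians". Section 3.2 says intervention-arm clinicians "will complete three surveys over approximately 21 months".

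**The concern.** The only safeguard in section 6.1.2 is tied to the primary outcome, which is fixed early in an infant's life. The assurance, however, covers every analysis, including outcomes that mature months or years later. Between the offer and the end of follow-up, control infants could be under the care of clinicians who have taken the education module and whose charting templates now prompt for peanut introduction and tolerance. Nothing in the plan delays the offer beyond primary data collection, censors control follow-up at the offer, or checks the result. The repeat analyses in section 13.4.4 deal with missing data, combined risk groups, adherence and peanut exposure, not with the offer date.

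At stake is whether the control arm still represents standard care. Peanut allergy might be noticed, acted on or charted differently part-way through follow-up in one arm only. Some control caregivers might be asked about peanut before the 12-month outcome is fixed. A control clinician trained before completing the KABF survey would no longer give a standard-care response.

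**Working it through.** The plan gives no figure for this exposure, so there is none to reproduce. Its power figures in section 13.7 are not at issue here.

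**Inputs.** The observation period is months 0 to 18 and at least one 4- or 6-month WCC falls within it (section 8.3). The oldest eligible infant is therefore 6 months old at month 0 (birth month −6), and the youngest is 4 months old at month 18 (birth month 14). Follow-up runs from age 4 to 30 months, which is 26 months. *Assumption:* births are uniform over these 20 months.

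**Offer month T.** It is not stated, so a range is needed:

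- Month 18, if assessment after either visit is enough, or if the control survey (which shares the offer's trigger) marks the end of the 18-month period.
- Month 20, when the youngest infant reaches 6 months: 14 + 6.
- Months 21 to 23, suggested by the clinician survey span and maximum duration.
- Month 26, if primary data collection includes the fallback caregiver surveys: 14 + 12.

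**Formulas.** Share of control infants under age x at the offer = (14 + x − T)/20, limited to 0–1. Share of follow-up time after the offer = 1 − E[min(T − b, 30) − 4]/26, where b is birth month.

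| Offer month | under 30 mo | under 12 mo | under 9 mo | follow-up after offer |
|---|---|---|---|---|
| 18 | 100% | 40% | 25% | 62% |
| 20 | 100% | 30% | 15% | 54% |
| 21 | 100% | 25% | 10% | 50% |
| 23 | 100% | 15% | 0% | 42% |
| 26 | 90% | 0% | 0% | 31% |

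For example, at T = 20 the share under 12 months is (14 + 12 − 20)/20 = 0.30. Mean age is then 16 months, so the follow-up share is 1 − (16 − 4)/26 = 0.54. The 100% entries follow from the eligibility window and need no uniformity assumption.

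**By endpoint.**

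- *Primary.* At month 18, (14 + 6 − 18)/20 = 10% of infants have not reached 6 months and could have that visit under iREACH. From month 20 none could. Fallback survey data must also be in.
- *Peanut allergy.* Some exposure is possible at every date in the table. It ends only at about month 44 (14 + 30).
- *Caregiver adherence.* Low-risk introduction by 12 months and high-risk continued feeding are open until about month 26. High-risk introduction by 7 months is barely open: 15% at month 18, 5% at month 20, none from month 21.
- *KABF.* The control survey and the offer share one trigger, and no rule sets their order.

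**Precision of the remedies, for an offer at months 20 to 23.** Restricting caregiver adherence to infants aged at least 12 months keeps k = 70% to 85%. With the plan's adherence ICC r = 0.07, the standard error ratio is √{[(1 + (km − 1)r)/(km)] / [(1 + (m − 1)r)/m]}. For an assumed survey response of 100% down to 25%, m is 333.3 to 83.3 (low-risk) and 16.7 to 4.2 (high-risk). The ratios are 1.003 to 1.029 and 1.038 to 1.152.

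For peanut allergy, the fraction f of diagnoses made before the offer is 46% to 58% if they are spread evenly over ages 4–30 months, or 70% to 83% if spread over 6–18 months (both assumptions). With the design effect unchanged, the standard error ratio for the log risk ratio is √{[(1 − fp)/(fp)] / [(1 − p)/p]}. With the plan's incidences this gives 1.10 to 1.48 (p = 1.5%) and 1.11 to 1.53 (p = 13.8%). The share of infants who have reached 24 months is (T − 18)/20, which is 10% at month 20 and 25% at month 23.

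**The case against.** The strongest reply is that being under 30 months is not the same as being exposed to anything that matters. The advisory, order set and counselling tools sit in the 4- and 6-month templates, which most or all enrolled control infants have passed by the offer. What remains is clinician education, plus two prompts to ask and chart. The 9-month prompt can reach only infants still under 9 months, and the 12-month prompt generally comes too late to change introduction by 12 months. This stands: the shares above are ceilings on exposure at each date, not effects. It does not rescue the assurance, because education and charting prompts can still act on a diagnosis counted to 30 months.

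Second, if the fallback surveys are part of primary data collection, the offer moves to about month 26 and the caregiver concern falls away. That also stands, which is why this part is conditional. Section 3.2 and the 21- and 23-month clinician spans favour an earlier date, and section 6.1.2 does not settle it.

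Third, the end-of-period placement of the control survey in Table 8.5.1 and section 11.1 suggests that it precedes the offer. It may, but sections 3.2 and 6.1.2 give both the same trigger.

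Fourth, section 3.4 separates diagnoses by source and certainty, which may help to reveal changed ascertainment. It would not restore a standard-care control arm. The detailed algorithm is in the Manual of Procedures, which was not available.

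A reader might go further and infer that the peanut-allergy effect will be diluted and power lost. The documents do not support that. Uptake by control practices is unknown, and closer charting could raise recorded diagnoses as readily as earlier introduction could lower them.

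**Conclusion.** The assurance is too broad as written. It is unsupported for peanut allergy on every plausible offer date. It is unsupported for between-arm caregiver adherence if the offer precedes about month 26, and for the between-arm KABF comparisons unless the control survey comes first. It holds for analyses within the intervention arm, such as KABF change over time, and for the primary analysis under the timing condition shown above. Allergist adherence, also planned in the manner of the primary model, was not assessed here and the plan should address it.

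The exposure figures rest on uniform accrual and an assumed offer month. They say how many control infants could be reached, not how many will be or with what result. It would be wrong to infer that the primary result is compromised or that the offer to controls should be withdrawn. This is a change that should be made; confidence is medium because the offer date and uptake are not given.

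**What to change.** 1. Limit the sentence in section 6.1.2 to the primary analysis and the analyses within the intervention arm. State separately whether allergist adherence is affected.
2. Define the offer date as no earlier than completion of all 6-month WCC data and of any survey data used to fill gaps in the primary outcome.
3. Require the control KABF survey before any control clinician receives the education module.
4. Log the activation date of each control practice.
5. Add two supportive sensitivity analyses, applied identically in both arms and keyed to the first control activation: (a) caregiver adherence in infants at least 12 months old on that date; (b) peanut allergy counting only diagnoses made before that date, with survey reports counted only if the survey was completed by then.

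The cost is a small amendment and one logged date per control practice, with no extra infants. For an offer at months 20 to 23, analysis (a) raises the standard error by about 0.3–3% in low-risk and 4–15% in high-risk infants, or more in the latter if few are tested. Analysis (b) raises the standard error of the log risk ratio by roughly 10–53% and drops most 24-month surveys, so it can only be supportive.

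Deferring the offer is an option for the sponsor to weigh, not a required change. Month 26 would close the caregiver question at a cost of 3 to 6 months' further wait compared with months 20 to 23. Month 44 would remove all exposure for peanut allergy but adds 21 to 24 months. It fits within the 51-month practice duration only if that clock starts at randomization, which is not stated.
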